4.8 Visits

4.8.1 Screening (Day -21 to Day 1)

Study subject will be informed about the study and the risks and benefits of participating. Information will be given, both verbally and in writing, and the Informed Consent Form (ICF) will be signed and dated by the subject and the Investigator before performing any study related procedures. Inclusion and exclusion criteria will be checked and demographic data, relevant medical history as well as relevant ongoing medication will be collected by the Investigator. Screening laboratory tests and ECG will be performed in accordance to Sections 8.2 and 8.3 to verify exclusion criteria 19. The blinded evaluator will make a live assessment to evaluate the wrinkle severity using the WSRS to verify inclusion criteria 4. Collection of AE will start when the ICF has been signed by the subject.

- Obtain Informed consent
- Obtain demographic data (initials, date of birth, gender, and ethnic origin)
- Interview for medical history and concurrent diseases
- Interview for concomitant medications and procedures
- Perform serum pregnancy test for all women of childbearing potential
- Screening laboratory assessments (hematology and serum chemistry)
- ECG
- Assess WSRS (by blinded evaluator) to verify inclusion criteria 4
- Assess eligibility (inclusion and exclusion criteria)

If the subject meets all of the inclusion criteria and none of the exclusion criteria a baseline visit will be performed immediately or scheduled within the next 21 days.

4.8.2 Baseline Visit - Initial treatment (Day 1)

The baseline visit can be performed in direct connection with the screening visit or at the latest 21 days after the screening visit.

If the screening and baseline visits are separated, the inclusion and exclusion criteria will be re-checked and if any changes have occurred in the health status, concomitant medication and procedures will be assessed before the subject can be included in the study.

Further, vital signs will be assessed, standardized pre-treatment photograph will be taken as described in Section 7.5, and a pregnancy test (U-HCG) will be performed in women of childbearing potential. Before treatment, the blinded evaluator will make a live assessment to evaluate the wrinkle severity on WSRS to obtain a baseline value.

- Interview for medical history and concurrent diseases
- Interview for concomitant medications and treatments
- Vital signs (pulse rate, blood pressure, respiratory rate, and axillary temperature)

 GALDERMA	Title 43CH1508 Clinical Study Protocol	Doc id MA-29708
--	---	----------------------------------

Effective date: 2017-07-05 06:37

Effective date:

Effective

Version: 5.0

- Perform urine pregnancy test for all women of childbearing potential (if ≥ 2 weeks since the pregnancy test performed at the screening visit)
- Assess WSRS to obtain a baseline value (by blinded evaluator)
- Confirm eligibility criteria

[figure not shown]
For each eligible subject, one NLF will be randomly assigned to treatment with Restylane Defyne (with lidocaine) and the opposite NLF to treatment with Restylane (without lidocaine). Treatment will be administered according to the instructions in Section 6.6. Any device deficiencies or AEs since last visit, during or after the treatment will be reported. **CCI**

CCI

[figure not shown]
- Randomize the subject and arrange for blinding of the subject
- Obtain a pre-treatment photograph (baseline)
- Perform treatment in the right NLF according to randomization (Section 6.6)

CCI

- Perform treatment in the left NLF according to randomization (Section 6.6)

CCI

- Interview for AE since last visit and evaluate the subject for post-treatment AEs
- Evaluate device deficiencies

4.8.3 Week 4 follow-up after initial treatment (Day 29 ± 3 days) / Optional touch-up

A follow-up visit will take place 4 weeks ($D29 \pm 3$ days) after the initial treatment. An optional touch-up treatment may be performed if optimal aesthetic improvement was not obtained.

Standardized photographs will be taken, WSRS will be completed by the blinded evaluator, **CCI**

any AEs since the initial treatment or change in medications used will be reported.

- Assess WSRS (by blinded evaluator)
- Obtain photographs

CCI

- Interview for concomitant medications and treatments
- Interview for AE

 GALDERMA	Title 43CH1508 Clinical Study Protocol	Doc id MA-29708
--	---	----------------------------------

A touch-up treatment may be performed at this visit if optimal aesthetic improvement was not obtained, i.e., subjects who did not improve ≥ 1 grade on WSRS in one or both NLFs as assessed by the blinded evaluator. The touch-up treatment will not be performed without the subject's verbal consent, if there are ongoing treatment-related AEs, or if optimal aesthetic improvement is already achieved.

A pregnancy test (U-HCG) will be performed in women of childbearing potential before the touch-up treatment (described in Section 6.6). Device deficiencies and AEs in connection to the treatment will be reported. **CCI**

A second 4-week follow up visit should be scheduled.

- Perform urine pregnancy test for all women of childbearing potential
- Perform treatment (as initially randomized, start injection in the right NLF)

CCI

- Evaluate the subject for post-treatment AEs
- Evaluate device deficiencies

4.8.4 Week 4 follow-up after touch-up treatment - only for subjects who received touch-up treatment (4 weeks ± 3 days)

A follow-up assessment will be performed 4 weeks after the touch-up treatment visit. Standardized photographs will be taken. WSRS will be completed by the blinded evaluator

CCI

any AEs since last visit or change in medications used will be reported.

- Assess WSRS (by blinded evaluator)
- Obtain photographs

CCI

- Interview for concomitant medications and treatments
- Interview for AE

4.8.5 Month 3 (± 7 days), 6 (± 7 days), and 9 (± 2 weeks) follow-up

Follow-up visits will be performed 3 months ± 7 days, 6 months ± 7 days, and 9 months ± 2 weeks after last treatment. Standardized photographs will be taken. WSRS will be completed by the blinded evaluator

CCI Any AEs since last visit or change in medications used will be reported.

- Assess WSRS (by blinded evaluator)

 GALDERMA	Title 43CH1508 Clinical Study Protocol	Doc id MA-29708
--	---	----------------------------------

- Obtain photographs
CCI

[figure not shown]
- Interview for concomitant medications and treatments
- Interview for AE

4.8.6 Month 12 (± 2 weeks) follow-up/ Final visit or Early termination

A final follow-up visit will be performed 12 months ± 2 weeks after the last treatment visit. In the case of subject withdrawal between regular visits (Section 5.5) the subject should, when possible, be scheduled for an early termination visit.

Standardized photographs will be taken. WSRS will be completed by the blinded evaluator
CCI

. Any AEs since last visit or change in medications used will be reported. A final pregnancy test (U-HCG) will be performed in women of childbearing potential.

- Perform serum pregnancy test for all women of childbearing potential
- Laboratory assessments (serum chemistry)
- Assess WSRS (by blinded evaluator)
- Obtain photographs
CCI

- Interview for concomitant medications and treatments
- Interview for AE

5 SUBJECTS

5.1 Subject information and informed consent

The PI or his/her authorized designee must always use the IEC approved subject information and ICF and it must not be changed without prior discussion with the Sponsor and approval from the applicable IEC.

It is the responsibility of the PI or his/her authorized designee to give each subject full and adequate verbal and written information regarding all aspects of the clinical study that are relevant to the subject's decision to participate throughout the study. The information should be given to the subject prior to inclusion in the study and should e.g., explain the purpose and procedures of the study, the duration and number of expected participants, possible risks involved, and the opinion of the IEC. The subject shall be informed that the participation is confidential and voluntary and that the subject has the right to withdraw from the study at any time, without any effect on his/her future medical care, treatment, or benefits to which the subject is otherwise entitled. The information shall be provided in a language clearly and fully understandable to the subject. The subject shall be given sufficient time to read and

 GALDERMA	Title 43CH1508 Clinical Study Protocol	Doc id MA-29708
--	---	----------------------------------

understand the informed consent form and to consider participation in the study. Before any study-related activities are performed, the informed consent form shall be personally signed and dated by the subject and the PI or his/her authorized designee responsible for conducting the informed consent process. The consent includes information that data will be collected, recorded, processed, and may be transferred to countries outside China. The data will not contain any information that can be used to identify the subject.

Photographs collected during the study will be analyzed and stored in a database by the Sponsor and its representatives in order to evaluate the effect of the treatment in the study. The subjects will be recognizable on the photographs, but their names will not be disclosed.

All signed ICF shall be filed in the Investigator file. The subject shall be provided a copy of the signed and dated informed consent form and any other written information.

The Investigator shall ensure that important new information is provided to new and existing subjects throughout the study.

5.2 Inclusion criteria

The subjects must meet the following criteria to be eligible for the study:

1. Signed and dated informed consent to participate in the study.
2. Men or women aged 18 years of age or older of Chinese origin.
3. Subjects willing to abstain from any other facial plastic surgical or cosmetic procedures below the level of the lower orbital rim for the duration of the study (e.g., laser or chemical resurfacing, needling, facelift, radiofrequency etc.).
4. Intent to undergo correction of both NLFs with a wrinkle severity in WSRS of either 3 on both sides or 4 on both sides, as assessed by the blinded evaluator.

5.3 Exclusion criteria

The presence of any of the following exclusion criteria will exclude a subject from enrolment in the study:

1. Known/previous allergy or hypersensitivity to any injectable HA gel.
2. Known/previous allergy or hypersensitivity to local anesthetics, e.g., lidocaine or other amide-type anesthetics.
3. History of severe or multiple allergies manifested by anaphylaxis.
4. Previous tissue revitalization treatment with laser or light, mesotherapy, radiofrequency, chemical peeling, or dermabrasion below the level of the lower orbital rim within 6 months before treatment.
5. Previous surgery (including aesthetic facial surgical therapy or liposuction) or tattoo in the area to be treated.
6. Previous tissue augmentation therapy or contouring with any permanent (non-biodegradable) or semi-permanent facial tissue augmentation therapy or autologous fat or permanent implant below the level of the lower orbital rim.

 GALDERMA	Title 43CH1508 Clinical Study Protocol	Doc id MA-29708
--	---	----------------------------------

7. Previous use of any HA based or collagen based biodegradable facial tissue augmentation therapy below the level of the lower orbital rim within 12 months before treatment.
8. Previous use of neurotoxins below the level of the lower orbital rim (crow's feet line is acceptable) within 12 months before treatment.
9. History of radiation or cancerous or pre-cancerous lesions (e.g., actinic keratosis) in the area to be treated.
10. Scars or deformities, active skin disease, inflammation or related conditions such as infection, perioral dermatitis, seborrheic dermatitis, eczema, rosacea, acne, psoriasis, and herpes zoster near or in the area to be treated.
11. Subjects with dental or oral status on visual inspection that in the opinion of the Investigator would make the subject unsuitable for inclusion, or Subjects with dental, oral or sinus surgery within past 12 months prior to the treatment visit or planned surgery, including dental implants, during the study period.
12. Ongoing infection in mouth or dentals.
13. Chronic infection in head and neck region.
14. History of or active autoimmune disease or connective tissue diseases such as systemic lupus erythematosus, rheumatoid arthritis, polymyositis, dermatomyositis, or localized or systemic scleroderma.
15. Tendency to form keloids, hypertrophic scars, or any other healing disorder.
16. History of bleeding disorders or treatment with anticoagulants or inhibitors of platelet aggregation e.g., aspirin or other non-steroid anti-inflammatory drugs (NSAIDs), Omega-3, or vitamin E within 2 weeks before treatment.
17. Treatment with chemotherapy, immunosuppressive agents, immunomodulatory therapy (e.g., monoclonal antibodies), systemic or topical (facial) corticosteroids within 3 months before treatment (inhaled corticoids are allowed).
18. Concomitant treatment with topical (facial) retinoids within 3 months or systemic retinoids within 6 months before treatment.
19. Any medical condition that in the opinion of the Investigator would make the subject unsuitable for inclusion (e.g., porphyria, a chronic, relapsing or hereditary disease that may affect the general condition or may require frequent medical treatment, any abnormal screening laboratory value or ECG, or psychiatric disorders).
20. Other condition preventing the subject from entering the study in the Investigator's opinion, e.g., subjects not likely to avoid other facial cosmetic treatments, subjects anticipated to be unreliable, unavailable or incapable of understanding the study assessments, or having unrealistic expectations of the treatment result.
21. Women who are pregnant or breast feeding, or women of childbearing potential who are not practicing adequate contraception or planning to become pregnant during the study period.
22. Study site personnel, close relatives of the study site personnel (e.g., parents, children, siblings, or spouse), employees, or close relatives of employees at the Sponsor Company.

 GALDERMA	Title 43CH1508 Clinical Study Protocol	Doc id MA-29708
--	---	----------------------------------

23. Participation in any other clinical study within 30 days before treatment.

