- To help avoid needle breakage, do not attempt to straighten a bent needle. Discard it and complete the procedure with a replacement needle.
- Do not reshield used needles. Recapping by hand is a hazardous practice and should be avoided.
- Discard unshielded needles in approved sharps collectors.

Contraindications

1. 瑞蓝 2 (Restylane) is contraindicated for patients with severe allergies manifested by a history of anaphylaxis, or history or presence of multiple severe allergies.
2. Do not use in patients with a history of hypersensitivity to streptococcal proteins, as the product may contain trace amounts of such material.
3. 瑞蓝 2 (Restylane) should not be used in the following situations:
 - Permanent implant or implant other than hyaluronic acid in the same area
 - Non-permanent implant placed in the same area during the previous 6-12 months
 - If no information is available on the type of implant
4. Do not use in patients with bleeding disorders or patients who are taking thrombolytics or anticoagulants.
5. Do not use where there is active disease, such as inflammation, infection or tumours, in or near the intended treatment site.

Warnings

1. 瑞蓝 2 (Restylane) is only intended for use as an intradermal implant. The product should not be used for breast site injections.
2. Do not resterilize 瑞蓝 2 (Restylane).
3. Do not inject intramuscularly or intravascularly. Aspiration prior to injection is recommended.
4. Unintentional introduction of soft tissue fillers into the vasculature in the face may lead to embolization, occlusion of the vessels, ischemia, necrosis or infarction at the implant site or in the area supplied by the blood vessels affected. Rare but serious adverse events include temporary or permanent vision impairment, blindness, cerebral ischemia or stroke. Stop the injection immediately if blanching occurs or if a patient complains of unusual pain or exhibits any symptoms suggestive of inadvertent intravascular injection. Such patients should receive prompt medical evaluation and attention.
5. 瑞蓝 2 (Restylane) should not be mixed with other products before implantation of the device.
6. The product is for single use only.
7. Do not use if package is damaged.

 GALDERMA	Title 43CH1508 Clinical Study Protocol	Doc id MA-29708
--	---	----------------------------------

Precautions

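### No exclusion criterion names streptococcal-protein hypersensitivity, a labelled contraindication to the Restylane every subject receives; separately, the touch-up window opens 3 days before that label's 4-week minimum

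*Protocol*

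**What the plan says.** **Eligibility.** Protocol Section 4.1 gives every subject Restylane Defyne in one fold and Restylane in the other. Section 6.2 says the Restylane is the Chinese commercial product, with its IFU in the carton and in Appendix 3. Contraindication 2 of that IFU is "Do not use in patients with a history of hypersensitivity to streptococcal proteins, as the product may contain trace amounts of such material".

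Three exclusion criteria in Section 5.3 deal with allergy. Criterion 1 is "Known/previous allergy or hypersensitivity to any injectable HA gel". Criterion 2 concerns local anaesthetics. Criterion 3 concerns severe or multiple allergies that showed themselves as anaphylaxis. Criterion 19 is discretionary: "Any medical condition that in the opinion of the Investigator would make the subject unsuitable for inclusion". The synopsis repeats the same 23 criteria.

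**Touch-up timing.** The Treatment Procedure part of the same IFU requires at least 4 weeks between the initial and the touch-up injection. The protocol's Touch-up definition, Table 1 and Section 4.8.3 set the touch-up visit at 4 weeks (Day 29) ± 3 days, with the injection given at that visit. Section 6.6.2.2 gives four weeks without a tolerance and prefers that both folds be treated.

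**The concern.** The protocol generally turns label contraindications into named checks. Both contraindications in the Restylane Defyne IFU (Appendix 2) appear in Section 5.3: allergy to HA filler or amide anaesthetics in criteria 1 and 2, and porphyria as an example in criterion 19. Section 2.2 also says that the sponsor's HA is made by *Streptococcus* bacteria, so the source of the hazard is in the protocol's own text. The corresponding Restylane contraindication nevertheless does not become a criterion.

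A person with this history who has never had a filler, and whose reactions were not anaphylactic, can pass every named criterion and then be given a product whose label says not to use it. No protocol deviation would be recorded. The stake is subject safety and label compliance in a trial meant to support registration in China (Section 2.5).

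The timing point is of the same kind but weighs less. A symmetric visit tolerance suits an assessment. Applied to a re-injection interval that the label gives as a minimum, it permits an early injection.

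**Working it through.** **1. The five Restylane contraindications (Appendix 3) against the 23 criteria (Section 5.3)**

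| IFU item | Subject | Nearest criteria | Match |
|---|---|---|---|
| 1 | Severe allergies with anaphylaxis, or multiple severe allergies | 3 | Partial: criterion 3 requires anaphylaxis |
| 2 | Streptococcal-protein hypersensitivity | none | None |
| 3 | Implants in the same area | 6, 7 | Partial: unknown implant type not named |
| 4 | Bleeding disorders, thrombolytics, anticoagulants | 16 | Partial: thrombolytics not named |
| 5 | Active disease in or near the site | 9, 10, 12, 13 | Covered |

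- Item 3 includes the case "If no information is available on the type of implant". Neither criterion 6 nor criterion 7 mentions it.
- Item 4 reads "Do not use in patients with bleeding disorders or patients who are taking thrombolytics or anticoagulants". Criterion 16 covers bleeding disorders and "treatment with anticoagulants or inhibitors of platelet aggregation".
- Tally: 1 of 5 with no counterpart, 3 of 5 partly mirrored, 1 of 5 covered. Criteria naming streptococcal proteins: 0 of 23.

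**2. Touch-up window against the IFU minimum**

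Inputs: initial injection on Day 1 (Section 4.1); touch-up on Day 29 ± 3 days (Section 4.8.3); IFU minimum of 4 weeks = 28 days (Appendix 3).

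- The protocol's nominal day: Day 1 + 28 = Day 29. This reproduces the stated day and meets the minimum.
- Window: 29 − 3 = Day 26 to 29 + 3 = Day 32, which is 7 days.
- Interval since injection = day number − 1.

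| Touch-up day | Days since injection | Shortfall against 28 |
|---|---|---|
| 26 | 25 | 3 |
| 27 | 26 | 2 |
| 28 | 27 | 1 |
| 29 to 32 | 28 to 31 | 0 |

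So 3 of the 7 permitted days fall short. With a window of Day 29 to Day 32, 4 days remain and none falls short.

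**3. Effect of the change on study duration**

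The latest touch-up stays at Day 32, which is 31 days after Day 1. Longest participation = 21 (screening) + 31 + 365 + 14 (Month 12 tolerance) = 431 days. At 30.44 days per month, 431 / 30.44 = 14.2 months, within the 14.5 months stated in Section 4.3.

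**The case against.** The strongest reply is that the protocol should be read together with its appendices. The Restylane IFU requires trained doctors to follow it strictly, to tell patients about contraindications, and to assess suitability before treatment. Criteria 19 and 20 give the investigator room to exclude. On that reading a contraindicated subject should be caught.

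These safeguards are real but partial. Criteria 19 and 20 rest on opinion, and their examples do not mention this condition. Section 4.5 records medical history only where the investigator judges it relevant, so nothing in the protocol prompts the question. The synopsis pointer to the Restylane IFU concerns the injection procedure and does not turn the label's contraindications into eligibility criteria. The consent form and site worksheets were not available, and nothing is claimed about them.

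On timing, it is fair to say that the 4-week interval is a note under Treatment Procedure, not a contraindication or warning, and that the documents name no harm from 25 to 27 days instead of 28. That is why this part carries less weight.

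A reader might also infer that the collagen rule conflicts with the label. Criterion 7 excludes "collagen based biodegradable facial tissue augmentation therapy below the level of the lower orbital rim within 12 months before treatment", so collagen placed earlier is allowed, while IFU item 3 bars "Permanent implant or implant other than hyaluronic acid in the same area" with no time limit. The documents do not support treating this as a conflict. The same item deals separately with non-permanent implants, using a look-back of 6 to 12 months. Criterion 7 takes the upper end of that range and applies it to everything below the lower orbital rim.

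**Conclusion.** Both points hold, and they concern the reference product only: the Restylane Defyne IFU lists neither this contraindication nor a minimum touch-up interval. The main point is one labelled contraindication that no eligibility criterion names. The lesser point is a window whose lower tail, Days 26 to 28, allows the Restylane fold to be re-injected 1 to 3 days early.

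Few subjects are likely to be affected. The documents give no prevalence for this hypersensitivity. Touch-up is limited to subjects who lack a one-grade WSRS improvement in at least one fold, who agree to it, and who have no ongoing treatment-related AE. The timing point arises only when the Restylane fold is re-injected.

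A reader might infer that contraindicated subjects will be treated, or that the efficacy result is in doubt. Neither follows. The documents show that the stated rules could let such a subject through, not that any will be, and the primary non-inferiority analysis does not change. The conclusion assumes that Section 5.3 is the operative eligibility checklist, as Section 4.4.1 implies by tying randomization to verification of those criteria.

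**What to change.** 1. Add a history of streptococcal-protein hypersensitivity to the exclusion criteria in Section 5.3 and the synopsis, with a matching screening question. Optionally name thrombolytics in criterion 16 in the same edit.
2. State in the Touch-up definition, Table 1 and Sections 4.8.3 and 6.6.2.2 that touch-up must not be given before Day 29 (window Day 29 to Day 32). Book the Week 4 visit on Day 29 to 32; otherwise a subject seen on Days 26 to 28 would have to return for the injection. These days lie inside the existing ± 3-day tolerance in the synopsis and Section 4.1, so neither of those needs to change.

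The cost is a short amendment with documented ethics committee approval (Section 12.3) and a minor eCRF update, since eligibility is verified before the eCRF assigns randomization. Screen failures may rise marginally, and touch-up scheduling narrows from 7 permitted days to 4. Maximum participation is unchanged.

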	
 7. Previous use of any hyaluronic acid based or collagen based biodegradable facial tissue augmentation therapy below the level of the lower orbital rim within 12 months before treatment. 8. Previous use of neurotoxins below the level of the lower orbital rim (crow's feet line is acceptable) within 12 months before treatment. 9. History of radiation or cancerous or pre-cancerous lesions (e.g., actinic keratosis) in the area to be treated. 10. Scars or deformities, active skin disease, inflammation or related conditions such as infection, perioral dermatitis, seborrheic dermatitis, eczema, rosacea, acne, psoriasis, and herpes zoster near or in the area to be treated. 11. Subjects with dental or oral status on visual inspection that in the opinion of the Investigator would make the subject unsuitable for inclusion, or Subjects with dental, oral or sinus surgery within past 12 months prior to the treatment visit or planned surgery, including dental implants, during the study period. 12. Ongoing infection in mouth or dentals. 13. Chronic infection in head and neck region. 14. History of or active autoimmune disease or connective tissue diseases such as systemic lupus erythematosus, rheumatoid arthritis, polymyositis, dermatomyositis, or localized or systemic scleroderma. 15. Tendency to form keloids, hypertrophic scars, or any other healing disorder. 16. History of bleeding disorders or treatment with anticoagulants or inhibitors of platelet aggregation e.g., aspirin or other non-steroid anti-inflammatory drugs (NSAIDs), Omega-3, or vitamin E within 2 weeks before treatment. 17. Treatment with chemotherapy, immunosuppressive agents, immunomodulatory therapy (e.g., monoclonal antibodies), systemic or topical (facial) corticosteroids within 3 months before treatment (inhaled corticoids are allowed). 18. Concomitant treatment with topical (facial) retinoids within 3 months or systemic retinoids within 6 months before treatment. 19. Any medical condition that in the opinion of the Investigator would make the subject unsuitable for inclusion (e.g., porphyria, a chronic, relapsing, or hereditary disease that may affect the general condition or may require frequent medical treatment, any abnormal screening laboratory value or ECG, or psychiatric disorders). 20. Other condition preventing the subject from entering the study in the Investigator's opinion, e.g., subjects not likely to avoid other facial cosmetic treatments, subjects anticipated to be unreliable, unavailable or incapable of understanding the study assessments, or having unrealistic expectations of the treatment result. 21. Women who are pregnant or breast feeding, or women of childbearing potential who are not practicing adequate contraception or planning to become pregnant during the study period. 22. Study site personnel, close relatives of the study site personnel (e.g., parents, children, siblings, or spouse), employees, or close relatives of employees at the Sponsor Company. 23. Participation in any other clinical study within 30 days before treatment.

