- Do not inject intravascularly. As for other injectable medical devices, inadvertent injection into or next to blood vessels could potentially lead to vascular occlusion or compression, ischemia and necrosis.
- Do not use in patients with bleeding disorders or in patients who are taking thrombolytics or anticoagulants.
- Do not inject this product into an area where an implant other than hyaluronic acid has been placed.
- Do not resterilize.
- Do not mix with other products.

VII. PRECAUTIONS FOR USE

General considerations relevant to injectable medical devices

- Knowledge of the anatomy of treatment site and special caution are required in order to avoid perforation or compression of vessels, nerves and other vulnerable structures.
- Injection procedures are associated with a risk of infection. Aseptic technique and standard practice to prevent cross-infections are to be observed.
- Special caution should be exercised when treating areas with limited collateral circulation, due to increased risk of ischemia.
- Special caution should be exercised in treating facial areas with limited soft tissue support or soft tissue cover, such as the periorbital area, to avoid formation of palpable lumps.
- Patients with pre-existing pigmented dark lower eye lid circles, thin skin and pre-existing tendency toward oedema formation are not suitable candidates for treatment of the lower periorbital region.
- Patients using immunosuppressants are not suitable candidates for treatment.
- Special caution should be exercised in treating patients with a tendency to form hypertrophic scars or any other healing disorders.
- Injection procedures can lead to reactivation of latent or subclinical herpes viral infections.
- Patients who are using substances that affect platelet function, such as aspirin and nonsteroidal anti-inflammatory drugs may, as with any injection, experience increased bruising or bleeding at injection sites.
- Patients with unattainable expectations are not suitable candidates for treatment.
- Do not use the product if the package is damaged.

 GALDERMA	Title 43CH1508 Clinical Study Protocol	Doc id MA-29708
--	---	----------------------------------

- Do not use the product if the contents of the syringe are cloudy.

Specific considerations relevant to the use of this product

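### Exclusion 7 lets in old collagen filler in the nasolabial fold that the appended Restylane Defyne instructions say not to inject over, and filler of unknown type is not addressed by name

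*Protocol*

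**What the plan says.** Two protocol criteria deal with earlier filler.

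- **Exclusion 6** has no time limit. It covers "any permanent (non-biodegradable) or semi-permanent facial tissue augmentation therapy or autologous fat or permanent implant below the level of the lower orbital rim".
- **Exclusion 7** has a 12-month limit and puts HA and collagen together. The synopsis wording is "Previous use of any hyaluronic acid based or collagen based biodegradable facial tissue augmentation therapy below the level of the lower orbital rim", followed by the same 12 months. Section 5.3 repeats the rule, for HA or "collagen based biodegradable facial tissue augmentation therapy below the level of the lower orbital rim within 12 months before treatment".

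The product instructions are appended to the protocol, and Sections 6.1 and 6.2 refer to them.

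- **Restylane Defyne** (Appendix 2, VI Warnings): "Do not inject this product into an area where an implant other than hyaluronic acid has been placed".
- **Restylane** (Appendix 3, Contraindication 3) lists three situations in which the product should not be used: "Permanent implant or implant other than hyaluronic acid in the same area"; "Non-permanent implant placed in the same area during the previous 6-12 months"; and "If no information is available on the type of implant".

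Under Sections 4.1 and 4.4.1 each subject receives Restylane Defyne in one fold and Restylane in the other.

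**The concern.** Section 5.3 and the appendices are parts of one protocol, and a site is expected to work to both. For a subject who had collagen in the fold more than a year ago, the eligibility list raises no objection, while the Defyne instructions say not to inject that area. For a subject with an old filler that nobody can identify, the eligibility list is silent, while the Restylane instructions say not to use the product.

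What is at stake is subject safety and consistent practice. Sites that read the documents differently would enrol different subjects. A subject let in under exclusion 7 breaches no eligibility criterion, so the inclusion/exclusion lines in SAP Table 2-1 would not flag the case, although that list is stated not to be exhaustive.

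**Working it through.** No arithmetic applies. The check sets the criteria beside the instructions, case by case.

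**Step 1. What the named criteria catch.** Exclusion 7 itself calls collagen filler biodegradable, so the check assumes such a filler falls under exclusion 7 and not under the permanent or semi-permanent class of exclusion 6. After 12 months exclusion 7 no longer applies. No other named criterion deals with earlier filler: exclusion 4 concerns revitalization treatments and exclusion 5 concerns surgery or tattoo. Exclusion 20, "Other condition preventing the subject from entering the study in the Investigator's opinion", is discretionary, and its examples do not mention earlier filler.

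**Step 2. Cases in the treatment area.**

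| History in the fold | Named exclusion | If Defyne goes there (Appendix 2) | If Restylane goes there (Appendix 3) |
|---|---|---|---|
| HA or collagen, within 12 months | No. 7 | Not reached | Not reached |
| HA, more than 12 months ago | None | No bar on HA | Outside the 6-12 month line |
| Collagen, more than 12 months ago | None | Not to be injected, no time limit | First line bars it; second line may be read as limiting the bar to 6-12 months |
| Unknown type, more than 12 months ago | None by name; no. 6 only if treated as unverifiable | No line on unknown type | Third line bars use |

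The first two rows are consistent. The last two are not.

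**Step 3. Whether allocation to sides removes the conflict.** Randomization follows verification of the criteria (Section 4.4.1), so eligibility is settled before the side is known.

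- Collagen in both folds: one of them always receives Defyne, so the conflict with Appendix 2 is certain.
- Collagen in one fold: the conflict is clear if that fold is assigned Defyne. If it is assigned Restylane, the answer depends on how the first two lines of Contraindication 3 are read together.
- Unknown filler in both folds: one always receives Restylane, so the third line always applies.
- Unknown filler in one fold: if that line is read as limited to the area of the implant, it applies only when that fold is assigned Restylane.

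Allocation therefore cannot be relied on to keep a subject clear of the restriction.

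**The case against.** Four points deserve weight.

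**The Restylane instructions may already allow the protocol's rule.** Collagen, being biodegradable, fits the line on non-permanent implants, and the 12 months of exclusion 7 match the upper end of its range. If the first line barred every non-HA implant for ever, the second would be left to cover HA alone, yet it is not worded that way. This stands as a fair reading. A reader might infer that both sets of instructions plainly forbid old collagen; the Restylane text does not settle that. The point does not answer the Defyne warning, which has no comparable line.

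**Unknown filler may already be screened out.** Section 4.4.1 requires the criteria to be verified, and Section 5.4 requires the investigator to confirm that no exclusion is met. Exclusion 6 is not limited to known permanent filler, whereas exclusions 1 and 2 do refer to known allergy. An investigator who cannot identify the filler may conclude that exclusion 6 cannot be cleared. So it would go too far to say that the protocol admits such subjects. What stands is that it does not name the case and leaves the outcome to inference.

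**Investigators hold the instructions and can decline.** Both are appended, Appendix 3 tells doctors to follow it strictly, and exclusion 20 gives a route to exclude. This lowers the practical risk. It does not remove the contradiction, because exclusion 20 neither requires exclusion nor mentions the case.

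**The product comparison is not shown to be affected.** A reader might infer that leftover material in one fold biases the result. Inclusion 4 requires grade 3 on both sides or grade 4 on both sides, which removes any asymmetry large enough to change a baseline grade, and side is randomized, so remaining asymmetry is not systematically tied to either product. The documents do not support a bias claim.

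**Conclusion.** The point holds as an inconsistency within the protocol on a matter of subject safety. The firm part is narrow: collagen placed in the fold more than 12 months ago passes every named criterion, while Appendix 2 says, with no time limit, not to inject there. Two lesser parts go with it: Appendix 3 is ambiguous on old collagen, and it bars use with an implant of unknown type, which exclusions 6 and 7 do not name.

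The size cannot be given. The documents contain no count of such subjects, and it may be small or zero. SAP Tables 5-5 and 5-6 are shells for any previous cosmetic procedure or implant; a reader might take them as a sign that such subjects are expected, but they do not show that.

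The conclusion assumes that a biodegradable collagen filler is not semi-permanent in the sense of exclusion 6, a term the protocol does not define, and that the appended instructions are meant to bind sites within the trial. It is worth correcting, but it does not put the primary analysis in doubt.

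**What to change.** The sponsor should reconcile exclusions 6 and 7, in Section 5.3 and the synopsis, with the implant-history lines of Appendix 2 (VI Warnings) and Appendix 3 (Contraindication 3). Sites should be left with one consistent instruction on two matters: previous collagen filler in the treatment area, and previous filler of unknown type there. This review does not say which rule should prevail or how the criteria should be worded.

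The cost is a few lines of text in a written amendment, with the ethics committee approval that Section 12.3 requires, and notice to sites. Screening already collects medical history, and the SAP already plans to tabulate previous procedures and implants by product and location, so little new data collection should be needed. Any effect on recruitment depends on how the sponsor resolves the conflict and cannot be estimated from the documents.
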